3 HYPOTHESES, OBJECTIVES, AND ENDPOINTS

This study will be carried out in 2 parts, a Phase 2 dose selection cohort and a Phase 3 confirmatory cohort. Each cohort includes a Base Period and an Extension Period.

In men and women aged 18 to 75 years (inclusive) with pulmonary arterial hypertension (PAH):

Primary Objectives	Primary Endpoints
 Phase 2 Cohort – to evaluate the effect of MK-5475 versus placebo on the pulmonary vascular resistance (PVR) at Week 12. Hypothesis: at least one MK-5475 dose is superior to placebo in reducing PVR from baseline at Week 12. 	PVR (centrally assessed)
 Phase 3 Cohort – to evaluate the effect of MK-5475 versus placebo on 6-minute walk distance (6MWD) at Week 12. Hypothesis: MK-5475 is superior to placebo in increasing 6MWD from baseline at Week 12. 	6MWD
Secondary Objectives	Secondary Endpoints
Phase 2 Cohort - to evaluate the effect of MK-5475 versus placebo on 6MWD at Week 12.	6MWD
Phase 2 Cohort - to evaluate the effect of MK-5475 versus placebo on hemodynamic parameters other than PVR at Week 12.	-Mean right arterial pressure (mRAP) -Cardiac index -Stroke volume index (SVI)
Phase 3 Cohort – to evaluate the effect of MK-5475 versus placebo on 6MWD at Week 24.	6MWD
Phase 3 Cohort - to evaluate the effect of MK-5475 versus placebo on the WHO functional PAH class at Week 12.	WHO functional class

Phase 2 and Phase 3 Cohorts (independently) – to evaluate the safety and tolerability of MK-5475.	-Adverse Events (AEs)-Discontinuation of study intervention due to AEs
CCI	

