Multiplicity	There are 3 treatment group comparisons that may be tested to address the primary hypothesis. Testing will be done in a sequential manner in descending order of MK-5475 randomized dose group, stopping at the point statistical significance is not achieved.		
Sample Size and Power	The planned sample size is approximately 164 participants. For the percent change from baseline in PVR at Week 12, the study has 85% power to demonstrate that MK-5475 380 μ g is superior to placebo group at an overall one-sided 2.5% alpha level.		

Phase 3 Cohort

Study Design Overview			
Treatment Assignment	 Participants (approximately 143/group) will be randomized in a 1:1 ratio between 2 treatment groups: 1) MK-5475 2) placebo matching MK-5475 		
Analysis Populations	Efficacy: FAS Safety: APaT		
Primary Endpoint	Change from baseline in 6MWD at Week 12		
Key Secondary Endpoints	N/A		
Statistical Methods for Key Efficacy Analyses	The difference (MK-5475 minus placebo) in change from baseline and the associated 95% CI and p -value will be provided based on a robust regression model. Missing 6MWD observations at Week 12 from participants in both treatment groups will be imputed based on the observed 6MWD observations at Week 12 from the placebo group.		
Statistical Methods for Key Safety Analyses	For analyses in which 95% CIs will be provided for between- treatment differences (MK-5475 minus placebo) in the percentage of participants with events, these analyses will be performed using the M&N method.		
Interim Analyses	No interim analyses are planned. (The primary analysis of efficacy data from the Phase 3 Cohort will occur when all participants in this cohort have completed [or discontinued prior to the end of] the Base Period. Although the Phase 3 Cohort will continue in the study [in the Extension Period], the Base Period analysis is not considered an interim analysis.)		
Multiplicity	As there is a single hypothesis test involving a single endpoint and a single between-treatment comparison, no multiplicity adjustment is required.		
Sample Size and Power	The planned sample size is approximately 286 participants. For the change from baseline in 6MWD at Week 12, the study has 90% power to demonstrate that MK-5475 is superior to placebo group at a one-sided 2.5% alpha level.		

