The difference (MK-5475 minus placebo) in percent change from baseline and the associated 95% CI and *p*-value will be provided. A *p*-value for the comparison of MK-5475 versus placebo <0.025 (one-sided) will be considered statistically significant contingent upon the multiplicity strategy (Section 9.8).

The following steps will be taken to perform the primary analysis, including imputation for missing data. Percent change from baseline in PVR at Week 12 is the response variable:

- 1. Define imputation model for different missingness patterns:
 - a. Obtain the worst outcome among all observed data.
 - b. Within the placebo group, for participants with both baseline and Week 12 data, fit an ANCOVA model including terms for treatment and WHO-FC (Class II and Class III/IV).

- 2. Impute missing data for different missingness patterns:
 - a. Death: for participants (in both treatment groups) who died before Week 12, the worst outcome among all observed data will be used to impute the missing Week 12 values.
 - b. Reasons other than death: For participants (in both treatment groups) missing the response variable, the fitted model in Step 1 will be used to impute the missing values.
- 3. Robust regression based on a Huber-type M estimator [Huber, P. J. 1973] will be performed for the imputed dataset. The model will include terms for treatment and WHO-FC (Class II and Class III/IV).
- 4. Steps 2 and 3 will be repeated 50 times to create 50 complete datasets and 50 sets of parameter estimates.
- 5. The final parameter estimate for the mean percent change will be the average of the 50 parameter estimates for the mean percent change from Step 4.
- 6. Steps 1 through 5 will be repeated 200 times based on bootstrap resampling. The resulting standard error for the mean percent change will be the standard error of the resulting parameter estimates obtained in the 200 bootstrap resampled datasets. The CI and *p*-value will be derived from a normal distribution based on the final parameter estimate and its standard error.

Two sensitivity analyses for percent change from baseline in PVR will be performed to assess the impact of missing data imputation. Within the same PMM structure in the primary analysis, for missing data due to reasons other than death, 1 analysis will use a tipping point approach and the other analysis will use an approach referred to as washout imputation.

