In the tipping point approach, missing values due to reasons other than death will be imputed based on the first step in the primary analysis with a positive adjustment Δ added for the MK-5475 group. The inference will be carried out for a range of values of Δ . The smallest value of Δ that renders the significant result into a non-significant result will be the tipping point value, which provides a measure of robustness of the primary result.

In the washout imputation approach, missing values due to reasons other than death in the MK-5475 group will be imputed from a normal distribution with the expected value set to the baseline value in the MK-5475 group and standard deviation computed based on the root mean squared error from the ANCOVA model described in the primary analysis. Missing values in the placebo group will be imputed in the same way as in the primary analysis.

Secondary Endpoint

The primary approach for addressing the mean change from baseline in 6MWD at Week 12 will use the same robust regression method described above for the primary endpoint. Summary statistics will be provided for other selected hemodynamic parameters listed in

Section 9.4.1. Table 5 summarizes the analysis strategy for efficacy endpoints in the Phase 2 Cohort.

Endpoint	Туре	Statistical Method	Analysis Population	Missing Data Approach
Primary Endpoint				
Percent Change from baseline in PVR at Week 12	P Sen Sen	RR RR RR	FAS FAS FAS	PMM-J2R PMM-Tipping point PMM-Washout
Secondary Endpoints				
Change from baseline in 6MWD at Week 12	Р	RR	FAS	PMM-J2R
Change from baseline in selected hemodynamic parameters at Week 12	Р	SS	FAS	N/A

Table 5Analysis Strategy for Primary and Secondary Efficacy Endpoints in the Phase
2 Cohort

6MWD=6-minute walk distance; FAS=full analysis set; J2R=jump-to-reference; N/A=not applicable; P=Primary PMM=pattern mixture model; PVR=pulmonary vascular resistance; RR=robust regression; Sen=Sensitivity; SS=summary statistics.

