The difference in change from baseline and the associated 95% CI and *p*-value will be provided (MK-5475 minus placebo). A *p*-value for the comparison of MK-5475 versus placebo <0.025 (one-sided) will be considered statistically significant.

The following steps will be taken to perform the primary analysis, including imputation for missing data. Percent change from baseline in 6MWD at Week 12 is the response variable:

- 1. Define imputation model for different missingness patterns:
 - a. Obtain the worst outcome among all observed data.
 - b. Within the placebo group, for participants with both baseline and Week 12 endpoint, an MMRM model including terms for treatment and WHO-FC (Class II and Class III/IV) will be fit.
- 2. The same procedure in Steps 2 through 6 described in Section 9.6.1.1 will be used for analysis.

Two sensitivity analyses of the estimand for change from baseline in 6MWD will be performed to assess the impact of missing data imputation. Within the same PMM structure in the primary analysis, for missing data due to reasons other than death, 1 analysis will use a tipping point approach and the other analysis will use an approach referred to as washout imputation. The analysis approaches are the same as in the 2 sensitivity analyses described in Section 9.6.1.1 except the missing data due to reasons other than death will be imputed by the MMRM model in the primary analysis.

As a supplemental analysis, the primary analysis will be repeated, excluding participants who participated in the Phase 2 Cohort.

Secondary Endpoint

The primary approach for addressing the mean change from baseline in 6MWD at Week 24 will use the same robust regression method in Section 9.6.1.1. Summary statistics will be provided for the proportion of participants whose WHO-FC is not worse at Week 12 relative to baseline. Table 6 summarizes the analysis strategy for efficacy endpoints in the Phase 3 Cohort.

Endpoint	Туре	Statistical Method	Analysis Population	Missing Data Approach
Primary Endpoint				
Change from baseline in 6MWD at Week 12	P Sen Sen	RR RR RR	FAS FAS FAS	PMM-J2R PMM-Tipping point PMM-Washout
Secondary Endpoints				
Change from baseline in 6MWD at Week 24	Р	RR	FAS	PMM-J2R
Proportion of participants whose WHO functional class does not worsen at Week 12 relative to baseline.	Р	SS	FAS	N/A

Table 6	Analysis Strategy for Primary and Secondary Efficacy Endpoints in the Phase
	3 Cohort

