Through 12 weeks post-randomization, drop-out is expected to be approximately 10% in each treatment group. However, based on the approach to missing data, all randomized participants per group are expected to be included in the primary analysis and are the basis for sample size and power calculations, accounting for imputation of missing data.

Power and sample size are based on the change from baseline in 6MWD at Week 12. Assuming the true change from baseline in 6MWD at Week 12 is 30 meters for MK-5475 versus 0 meters for placebo, the assumed change from baseline in 6MWD at Week 12 using J2R to impute missing data would be 27 meters for MK-5475 versus 0 meters for placebo. The assumed standard deviation of the difference of change from baseline in 6MWD at Week 12 between each MK-5475 and placebo is 70 meters. Under these assumed change and standard deviation, a sample size of 143/group provides 90% power to demonstrate superiority for each of the MK-5475 treatment comparisons using a one-sided alpha=0.025.

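### The Phase 3 tipping-point analysis inherits the positive shift written for PVR; on 6MWD that shift favours MK-5475, so as written it moves away from any tipping point

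*Combined protocol and SAP*

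**What the plan says.** Section 9.6.1.1 sets out the tipping-point analysis for percent change in PVR. Values missing for reasons other than death are "imputed based on the first step in the primary analysis with a positive adjustment" applied in the MK-5475 group. The analysis is repeated over a range of shifts, and the smallest shift that "renders the significant result into a non-significant result will be the tipping point value". That value is offered as the measure of how robust the primary result is.

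Section 9.6.1.2 carries this over to 6MWD: "The analysis approaches are the same as in the 2 sensitivity analyses described in Section 9.6.1.1". It then makes a single change, which concerns only the model used to fill in the missing values. No other exception is made, and no other section restates the direction of the shift for 6MWD.

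The direction of benefit is clear elsewhere. The Section 3 hypothesis is that "MK-5475 is superior to placebo in increasing 6MWD from baseline at Week 12", and the Phase 3 table in Section 9.1 gives the contrast: "The difference (MK-5475 minus placebo) in change from baseline and the associated 95% CI".

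**The concern.** A tipping-point analysis asks how bad the unseen outcomes on the active arm would have to be before the conclusion fails, so the shift must work against the drug. For PVR an upward shift does. For 6MWD an upward shift lengthens the imputed walks on MK-5475 and enlarges the treatment difference. The inherited rule then searches in a direction where a significant result does not become non-significant in practice, and even a borderline result looks secure.

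This is one of only two missing-data sensitivity analyses planned for the confirmatory endpoint (Table 6). If it is run as written, finding no tipping point could be read as strong robustness. If the slip is noticed only at that stage, the shift would be respecified with the treatment result already known.

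**Working it through.** **Inputs.** From Section 9.9.1 (Phase 3): 143 per group, 30 m versus 0 m before imputation, 27 m versus 0 m after jump-to-reference imputation, SD 70 m, one-sided alpha 0.025, power 90%. The same section states: "Through 12 weeks post-randomization, drop-out is expected to be approximately 10% in each treatment group". I take that 10% as the share of missing Week 12 values.

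**The plan's own figures.** 30 × 0.90 = 27 m. With 143 per group, 27 m and SD 70 m, power is 90.3% (stated: 90%). Both reproduce.

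**Effect of the shift, closed form.** Let p be the missing share, Δ the shift added to imputed MK-5475 values, d the difference at Δ = 0 and n = 143. The difference becomes d + pΔ, and the shift adds p(1 − p)Δ² to the variance in the MK-5475 arm:

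z(Δ) = (d + pΔ) / √{[2 × 70² + p(1 − p)Δ²] / n}

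At Δ = 0 the SE is 70√(2/143) = 8.28 m, so significance needs a difference above 1.96 × 8.28 = 16.2 m. With p = 0.10:

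| Δ (m) | z, d = 27 m | z, d = 17 m (borderline) |
|---|---|---|
| −100 | 1.97 | – |
| −50 | 22/8.37 = 2.63 | 12/8.37 = 1.43 |
| 0 | 3.26 | 2.05 |
| +50 | 32/8.37 = 3.82 | 22/8.37 = 2.63 |
| +100 | 37/8.65 = 4.28 | 27/8.65 = 3.12 |

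Setting the derivative to zero, z increases until Δ = 2 × 70² / [d(1 − p)], which is 9800 / (27 × 0.9) ≈ 403 m for d = 27 m. Beyond that it falls towards √[np/(1 − p)]: 3.99 at 10% missing and 2.74 at 5%. Both limits exceed 1.96, so under this formula a significant result never tips upward at those rates. At 2% missing the limit is 1.71, but z is still 3.28 at +1000 m. Eligible baseline walks are 150 to 500 m, so that exception is an artefact.

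**Same rule on PVR, for contrast.** With 41 per group, −27 points and SD 40 points, SE = 40√(2/41) = 8.83 and the critical difference is −17.3. Solving −27 + 0.10Δ = −17.3 gives Δ ≈ +97 points (SE held fixed). For PVR the positive shift does reach a tipping point.

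**Simulation closer to the planned method.** I simulated 600 trials per missing rate with normal changes (means 30 m and 0 m, SD 70 m) and 14 (10%) or 7 (5%) values per arm missing completely at random. Missing values in both arms were drawn from the placebo model, with the shift added to MK-5475 draws only. Each dataset was analysed by Huber regression on treatment and WHO-FC. Section 9.6.1.1 says "Steps 1 through 5 will be repeated 200 times based on bootstrap resampling"; the SE was obtained that way in each trial, with the placebo model refitted in every resample. Simplifications: a Week 12 placebo model in place of the MMRM, 10 imputations instead of 50, no deaths, and a 50/50 WHO-FC split with no effect.

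| Shift (m) | Mean z, 10% missing | Mean z, 5% missing |
|---|---|---|
| −100 | 2.20 | 2.86 |
| −50 | 2.69 | 3.11 |
| 0 | 3.33 | 3.43 |
| +50 | 3.95 | 3.73 |
| +100 | 4.36 | 3.93 |

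Trials significant at zero shift that lost significance:

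| | +50, +100 or +300 m | −50 m | by −100 m |
|---|---|---|---|
| 10% missing, 553 significant | 0 | 99 (18%) | 198 (36%) |
| 5% missing, 560 significant | 0 | 35 (6%) | 66 (12%) |
| 10% missing, z from 1.96 to 2.5 (91) | 0 | 87 | 91 |
| 5% missing, z from 1.96 to 2.5 (67) | 0 | 35 | 64 |

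The Monte Carlo SE of the percentages for all significant trials is about 1 to 2 points. The lowest z seen at any tested positive shift among significant trials was 2.52 (10% missing) and 2.23 (5% missing). The shifts illustrate direction; they are not a proposed range.

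**The case against.** The strongest reply is that the intention is plain. A tipping point is defined as the loss of significance, and for 6MWD only a downward shift can sensibly produce that. On this view the sign is a drafting slip with one reasonable resolution, and a competent programmer would reverse it. The supplemental SAP, which is not available here, may already do so, and Section 9 provides for documenting changes to non-confirmatory analyses there. The claim that the slip would surface only after unblinding is conjecture.

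Other protection also remains. The primary analysis imputes missing MK-5475 values from placebo, deaths receive the worst observed outcome, and the washout analysis uses no shift. Missing data may be below 10%, because Section 8.11.5 asks participants who stop treatment to return at Week 12. At the design values even the corrected analysis tips only near −100 m. Finally, under the Huber estimator z does not keep climbing: in a single illustrative dataset it was 4.22 at +100 m and 4.21 at +400 m.

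Most of this is fair and limits the consequence. It does not remove the error. A positive adjustment that is added is an arithmetic instruction. Section 9.6.1.2 adapts the inherited method for 6MWD and changes only the model, and nothing in the documents sends the direction of the shift to the supplemental SAP. The levelling-off at large shifts does not bring significance into doubt. The 5% results show the same direction with smaller numbers.

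**Conclusion.** The concern holds. As written, the Phase 3 tipping-point analysis shifts imputed 6MWD values in favour of MK-5475 and so cannot, in practice, find the point it is meant to find. It is almost certainly a carry-over from the PVR text, but the stated rule is the reverse of what is needed.

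The direction follows from the text alone. The size rests on the plan's 27 m, 70 m and 143 per group, on 5% or 10% missing values, and on the simplifications listed with the simulation. Under those assumptions no significant trial tipped at the positive shifts tested, while 12% (5% missing) to 36% (10% missing) did by −100 m once the sign was reversed.

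The effect is confined to one sensitivity analysis. It should be corrected before Phase 3 unblinding, but it does not threaten the primary conclusion.

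**What to change.** In Section 9.6.1.2, state that for 6MWD the adjustment is subtracted from imputed MK-5475 values, that is, towards a shorter distance.

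State the unit as well. The analysis steps in that section name percent change in 6MWD as the response, whereas the endpoint and the sample-size calculation use change in metres, so the scale of the shift is currently unclear.

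It would also help for the sponsor to fix and justify the range of shifts before Phase 3 unblinding, and to say that finding no tipping point within that range is a reportable result. These two additions are secondary to the sign.

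The cost is one or two sentences, with no extra data and no change to the primary analysis.

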9.6.2 Analysis Methods for Safety Analyses

Safety analyses of the Phase 2 Cohort and the Phase 3 Cohort will be performed separately. The analysis methods for safety analyses are the same for both cohorts. The analyses at the end of the Extension Period will include data collected in both the Base and Extension Period of each study cohort.

Safety and tolerability will be assessed by clinical review of all relevant parameters including AEs, laboratory tests, vital signs, PFTs, and ECG measurements. Except where noted otherwise, the same analyses will be performed at the end of the Base Period and at the end of the Extension Period.

The Treatment Period will include all data from randomization up to 14 days after the last dose of study medication. All safety endpoints will be analyzed for the time frame consisting of the treatment period + 14-day post-treatment follow-up, except SAEs. For SAEs, the analysis will include all post-treatment follow-up.

AEs will be coded using the standard MedDRA and grouped according to SOC.

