8.11.6 Final Visit

If applicable, participants will continue study intervention until Week 12 (participants in Phase 2 Cohort Base Period) or until the Final Visit (participants in Phase 2 Cohort Extension Period and in Phase 3 Cohort). For Phase 3 Cohort, the Final Visit will be conducted for all participants when the planned number of clinical worsening events is reached and is announced by the Sponsor. Participants in the Phase 2 Cohort Extension Period and in the Phase 3 Cohort who prematurely discontinue study intervention are required to attend the Final Visit for collection of clinical events and all assessments and procedures outlined in the SoA.

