9.6.2.1 Overall Safety Assessment

The overall safety evaluation will include a summary by treatment group of the number and percentage of participants with at least one AE, drug-related AE, SAE, and drug-related SAE, as well as who discontinued from study intervention due to an AE and who had an AE resulting in death. Point estimates and 95% CIs for the differences between treatment groups in the percentages of participants with these events will be provided.

The number and percentage of participants with specific AEs will also be provided. Point estimates and 95% CIs for the differences between treatment groups in the percentages of participants with specific AEs will be provided for AEs that occur in at least 4 participants in any treatment group. This threshold for the numbers of events was chosen because the 95% CI for the between-group difference in percent incidence will always include zero when fewer participants per group have events and thus would add little to the interpretation of potentially meaningful differences.

Point estimates and 95% CIs will be provided for the percentage of participants with safety parameters that meet predefined limits of change based on the same criteria used above for the specific AEs.

CIs for between-treatment group differences will be provided using the Miettinen and Nurminen (M&N) method [Miettinen, O. and Nurminen, M. 1985]. These CIs will not be adjusted for multiplicity and should be regarded only as helpful descriptive measures for the review of the safety profile and not as a formal method for assessing statistical significance of between-group differences. Rainfall plots with point estimates and 95% CIs will be displayed for AEs that occur in at least 4 participants in any treatment group.

Assessment of Safety Topics of Interest

Safety topics of interest include AEs of symptomatic hypotension, pulmonary hemorrhage, and hemoptysis. The safety topics of special interest will be summarized by treatment group of the number and percentage of participants. Point estimates and 95% CIs for between-group differences will be provided based on the criteria described above for specific AEs.

A summary of the analysis strategy for safety parameters is provided in Table 7.

Analysis Part	Safety Endpoint	Descriptive Statistics	95% Between- group CIª	Graphical Display ^a
Overall Safety Assessment	Any AE	Х	Х	
	Any serious AE	Х	Х	
	Any drug-related AE	Х	Х	
	Any serious and drug-related AE	Х	Х	

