	Discontinuation due to AE	Х	Х	
	Death	Х	Х	
pan gro Sp	SOCs, PDLCs (incidence ≥4 of participants in any treatment groups)	Х	Х	
	Specific AEs (incidence ≥4 of participants in any treatment groups)	Х	Х	Х
	Specific AEs, SOCs, PDLCs (incidence <4 of participants in any treatment groups)	Х		
	Change from Baseline results (laboratory tests, ECGs, vital signs)	Х		
Safety Topics of Special Interest	Symptomatic hypotension Pulmonary hemorrhage Hemoptysis	Х	Х	Х

 Table 7
 Analysis Strategy for Safety Parameters

AE=adverse event; CI=confidence interval; ECGs=electrocardiograms; PDLC=predefined limit of change; SOC=system organ class; X=results will be provided.

^a 95% between-group CI and graphical display will not be provided for the analysis of the Phase 2 Cohort Extension Period.

[figure not shown]

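### At the end of the Phase 3 Extension, arms are compared on crude percentages of participants with events; exposure-adjusted rates should be added for endpoints whose window follows the last dose

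*Combined protocol and SAP*

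**What the plan says.** Section 9.6.2 sets one safety method for both periods: with exceptions to be noted, "the same analyses will be performed at the end of the Base Period and at the end of the Extension Period". The later analysis is cumulative: "The analyses at the end of the Extension Period will include data collected in both the Base and Extension Period of each study cohort".

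Section 9.6.2.1 supplies the measure: "Point estimates and 95% CIs for the differences between treatment groups in the percentages of participants with these events will be provided". It also supplies the interval: "CIs for between-treatment group differences will be provided using the Miettinen and Nurminen (M&N) method". The same section says these intervals "should be regarded only as helpful descriptive measures for the review of the safety profile".

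Table 7 footnote a makes one exception: "95% between-group CI and graphical display will not be provided for the analysis of the Phase 2 Cohort Extension Period". The Phase 3 Extension therefore keeps its intervals and plots.

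On the window, Section 9.6.2 states: "The Treatment Period will include all data from randomization up to 14 days after the last dose of study medication". It excepts SAEs, which are analysed over all follow-up after treatment.

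Phase 3 treatment lasts 12 weeks plus up to 60 months (Section 1.1; Section 6.1, Table 2). The end is event-driven: "the Final Visit will be conducted for all participants when the planned number of clinical worsening events is reached" (Section 8.11.6). Section 9.12 summarises exposure separately, in puffs. No rate per person-time and no time-to-first-event safety analysis is specified.

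**The concern.** A difference in crude percentages is a fair summary when everyone is observed for the same fixed time, as in the Base Period. Over several years, a participant who stays on treatment has more time in which to record a first event. For non-serious AEs, the safety topics of interest (symptomatic hypotension, pulmonary hemorrhage, hemoptysis) and predefined limits of change, observation ends shortly after the last dose. If one arm stays on treatment longer, part of the difference shown is only longer observation.

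The documents contain routes to unequal stopping in either direction. A need for a prohibited medication may lead to discontinuation (Section 6.5), and need for additional treatment is also part of disease progression (Section 10.1.4.4); if the drug works, this could shorten placebo exposure. An SAE judged related to study intervention ends treatment (Section 7.1), which could shorten MK-5475 exposure. In the first case MK-5475 would look less safe than it is; in the second, a real excess would be understated. Safety is a secondary objective of the Phase 3 Cohort, and these rows are its planned long-term between-group display.

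**Working it through.** **The plan's own figure.** The documents give no figure for the safety comparison. The only design figure behind the arm size is the Phase 3 power in Section 9.9.1: 143 per group, 27 m against 0 m, SD 70 m, one-sided alpha 0.025. Standard error = 70 × √(2/143) = 8.28. Power = Φ(27/8.28 − 1.96) = Φ(1.30) = 90.3%, against 90% stated. It reproduces, so 143 per arm is used below.

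**Inputs from the documents.** 143 per arm, 1:1; non-SAE window of last dose + 14 days; Extension of up to 60 months, ending at an event-driven common cutoff.

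**Assumptions, because the documents give no Extension values.** First-event hazard λ of 0.03, 0.10 or 0.30 per year, equal in both arms. Constant discontinuation rate d of 0.10 per year in one arm and 0.20 or 0.30 in the other. Time T from randomization to cutoff uniform over 3 to 5 years, or over 1 to 3 years.

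**Formula.** With w = 14/365.25 = 0.0383 years,

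P(event) = 1 − e^(−λw) × [ d/(d+λ) × (1 − e^(−(d+λ)T)) + e^(−(d+λ)T) ], averaged over T.

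**One case by hand, at T = 4 years and λ = 0.30.**
- d = 0.10: e^(−1.6) = 0.2019. The bracket is 0.25 × 0.7981 + 0.2019 = 0.4014. P = 1 − 0.9886 × 0.4014 = 60.3%.
- d = 0.30: e^(−2.4) = 0.0907. The bracket is 0.50 × 0.9093 + 0.0907 = 0.5454. P = 1 − 0.9886 × 0.5454 = 46.1%.
- The gap is 14.2 points. Averaged over T from 3 to 5 years it is 14.1.

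**Cutoff at 3 to 5 years, true rate ratio 1.** Mean exposure is 39.4 months at d = 0.10, 32.9 at 0.20 and 27.8 at 0.30. The last column uses expected counts rounded to whole participants, so its point difference can depart slightly from the third column.

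| d (per year) | λ | Crude % (difference, points) | Counts of 143; M&N 95% CI |
|---|---|---|---|
| 0.10 v 0.20 | 0.03 | 9.4 v 7.9 (+1.5) | 13 v 11; −5.3 to 8.2 |
| 0.10 v 0.20 | 0.10 | 27.7 v 23.4 (+4.2) | 40 v 34; −6.0 to 14.3 |
| 0.10 v 0.20 | 0.30 | 59.9 v 52.1 (+7.8) | 86 v 74; −3.1 to 19.7 |
| 0.10 v 0.30 | 0.03 | 9.4 v 6.7 (+2.7) | 13 v 10; −4.5 to 8.8 |
| 0.10 v 0.30 | 0.10 | 27.7 v 20.1 (+7.5) | 40 v 29; −2.3 to 17.6 |
| 0.10 v 0.30 | 0.30 | 59.9 v 45.8 (+14.1) | 86 v 66; 2.4 to 25.2 |

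Only the last interval excludes zero.

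**Other settings.**
- Cutoff at 1 to 3 years: +0.5 to +3.4 points (0.10 v 0.20) and +0.9 to +6.3 points (0.10 v 0.30).
- Week 12: at most 0.1 point at these hazards, and 0.4 at λ = 1.0.
- Equal discontinuation: 0 at every setting.
- Very common events saturate: at λ = 1.0 and 0.10 v 0.30 with a 3 to 5 year cutoff, 89.9% v 77.3%, a gap of 12.7 points.
- A true benefit can look like harm: hazards of 0.08 v 0.10 (ratio 0.8) with discontinuation 0.10 v 0.30 and a 3 to 5 year cutoff give 22.9% v 20.1%.

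**The same data as rates.** In the last table row, person-years at risk per participant equal P/λ: 0.599/0.30 = 2.00 and 0.458/0.30 = 1.53. Expected first events are 85.7 in 285.6 person-years and 65.5 in 218.4 person-years, so 30.0 per 100 person-years in both arms. This equality follows from the constant-hazard model.

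**The case against.** The strongest reply is that the bias is conditional and the intervals carry no decision. Both parts stand. Section 9.9.1 assumes the same 10% drop-out in each arm to Week 12, and nothing is said about the Extension. Staggered entry and a common cutoff are balanced by randomization. Clinical worsening is not itself a listed mandatory reason to stop treatment in Section 7.1. At one inhalation a day, puffs approximate treatment days, so a difference in exposure would be visible. The Week 12 comparison has its own database lock and report (Section 9.2) and is practically unaffected. An event that makes a participant stop is still counted, and has its own row in Table 7. Visible exposure, however, does not correct the difference displayed next to it.

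The sentence in Section 9.6.1 that rules out statistical comparisons in either Extension does not answer the point. It stands under efficacy methods, and footnote a of Table 7 would be unnecessary if it covered safety.

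Three stronger readings are tempting and not supported:
- A reader might infer that every safety row is cut at last dose. Section 9.6.2 excepts SAEs, so the serious-AE and serious drug-related rows, and deaths due to AEs, are not cut there in the planned analysis.
- A reader might infer that the plan will make MK-5475 look less safe. The documents give no basis for saying which arm stays on treatment longer, or that either does.
- A reader might treat the intervals as tests. With an assumed hazard of 0.25 per year and mean exposure of 2.5 v 2.0 years, a normal approximation puts the interval wholly above zero in about 23% of trials instead of 2.5%. Section 9.6.2.1 calls the intervals descriptive, so this is not a Type I error rate of the plan.

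**Conclusion.** The concern holds in a limited form. For non-serious AEs, safety topics of interest and predefined limits of change at the end of the Phase 3 Extension, the planned between-group measure takes no account of time at risk, although the window follows time on treatment. With no true difference, the spurious gap is about 1.5 to 14 points against the longer-treated arm at a 3 to 5 year cutoff. That range rests on the assumed hazards of 0.03 to 0.30 per year and assumed discontinuation of 10% against 20 to 30% per year; it shrinks with an earlier cutoff and is zero if discontinuation is equal. No formal test and no Base Period result is affected. How complete the SAE rows will be is a separate question: Section 9.6.2 analyses all post-treatment follow-up, Section 8.4.1 requires reporting of all SAEs only through 14 days after stopping, and Section 8.11.5 has AEs and SAEs reviewed at later visits. This is a cheap improvement, not a fault that undermines the trial.

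**What to change.** In Section 9.6.2 and Table 7, for the end-of-Extension Phase 3 summaries:
- Add exposure-adjusted incidence rates (first events per 100 person-years at risk), with rate difference and 95% CI, as the main between-group measure for non-SAE endpoints. Keep the crude percentages alongside.
- For SAEs, use person-time over the full post-treatment follow-up that Section 9.6.2 already sets; do not shorten it to the treatment window. Reconcile that window with the reporting period in Section 8.4.1 and the visits in Section 8.11.5.
- Keep the Miettinen-Nurminen differences for the 12-week Base Period.
- In Section 9.12, report exposure in person-years as well as puffs.
- Clarify the window wording. Section 9.6.2 defines the Treatment Period as already running to 14 days after the last dose, then adds 14 days of follow-up to it. Reading it as 28 days multiplies each gap above by a further e^(−λw): the largest becomes 14.1 × 0.9886 = 13.9 points.

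The cost is some SAP wording and one extra table set. The rates assume a roughly constant hazard, and they do not remove bias from stopping that is itself related to the risk of an event.
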